4.2 Inclusion Criteria

- Males or females aged between 8 years to less than 16 years at time of screening who meet NIH diagnostic criteria for NF1 (Appendix 1);
- Participants must have a full-scale IQ of 70 or above. In cases where there is a statistically significant difference between verbal IQ and performance IQ (.05 level as determined by Table B3 in the WASI manual), participants will be eligible if at least one of these quotients is 70 or above;
- Participants must have a cognitive impairment defined as having a score of at least one standard deviation or more below the population mean on one or more of the primary objective outcome measures (i.e., impaired on a measure of visual spatial learning and/or sustained attention);
- Participants must be medically stable;
- Participants who are on a stable dose of methylphenidate and/or dextroamphetamines for at least one month prior to screening and who will remain on the same dose for the duration of the study (see Section 4.3 for exclusion criteria regarding other psychotropic medication, i.e. medication capable of affecting the mind, emotions or behavior)
- Hepatic function: Participants must have adequate liver function defined as at least 3 of the 4 liver function tests to be $< 2 \times$ upper limit of normal for age according to institution standards (AST, ALT, Direct bilirubin, Indirect bilirubin [computed from total bilirubin and direct bilirubin]) and no tests should be $>5 \times$ upper limit of normal for age;
- Renal function: Participants must have adequate renal function defined as serum creatinine $\leq 1.5 \times$ upper limits of normal for age, and BUN $\leq 1.5 \times$ upper limits of normal for age or a creatinine clearance of greater than 70 ml/m/1.73m²;
- Hematologic function: Participants must have an absolute neutrophil count of $> 1,000$, a hemoglobin ≥ 10 gms/dl, and a platelet count $> 100,000$ on study entry;
- Participants must sign all required documents, including informed assent and HIPAA documents;
- Female participants of childbearing age should not be pregnant, must have a negative pregnancy test before initiation of treatment, and take appropriate birth control precautions to participate in this study.

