5.1.2 History and Physical Examination

A complete medical history and physical examination (including neurological examination) will be performed initially to confirm each participant's NF1 diagnosis and to document any complications that they might have from the disease. Height, weight, head circumference, blood pressure, and pulse will be recorded. Patients will also be given a list of medications to avoid while on this study. To be eligible participants must have not taken any stimulant medications for at least 30 days or more and agree to remain off stimulant medication for the duration of the study.

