5.2 Treatment Visits

5.2.1 Dose Schedule and Prescription

Eligible participants will be dispensed 20mg of Lovastatin or the placebo at the initiation of treatment. Participants will be given directions to take the medication once daily after dinner time. Given that Lovastatin has a strong odor; participants will be required to swallow the capsule whole without breaking the seal. Participants will take one tablet (20mg Lovastatin) per dose for two weeks; and increase to two tablets per dose during the following weeks (40 mg Lovastatin). Participants will continue on the same dosage for a total of 14 weeks. In order to assess medication compliance, participants will be required to complete pill diary forms. All participants will be provided with a complete list of medications and products that have detrimental interactions with Lovastatin that must be completely avoided while being treated with Lovastatin (see Appendix 6).

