6.0 Pharmaceutical Information

6.1 Pharmacokinetics

Lovastatin is one of the first-generation statins and therefore has a large body of safety and pharmacokinetic data from clinical trials and general use for hyperlipidemia (Corsini, et al., 1995a).

1. It is a lactone that is readily hydrolyzed in vivo to the corresponding b-hydroxyacid, a potent inhibitor of HMG-CoA reductase. Inhibition of HMG-CoA reductase is the basis for an assay in pharmacokinetic studies of the b-hydroxyacid metabolites (active inhibitors) and, following base hydrolysis, active plus latent inhibitors (total inhibitors) in plasma following administration of Lovastatin;
2. Following an oral dose of ¹⁴C-labeled Lovastatin in men, 10% of the dose was excreted in urine and 83% in feces. Plasma concentrations peaked at two hours and declined rapidly to about 10% of peak by 24 hours post dose;
3. Lovastatin is highly bound (>95%) to human plasma proteins. Animal studies demonstrated that Lovastatin crossed the blood brain and placental barriers;
4. The major active metabolites present in human plasma are the b-hydroxyacid of Lovastatin, its 6^{''}-hydroxy derivative, and two additional metabolites. Peak plasma concentrations of both active and total inhibitors were obtained within two to four hours of dose administration;
5. The recommended dose in children 10 to 17 years old is 10-40 mg/day (Merck & Co., Inc, 2007);
6. It is metabolized in the liver by the cytochrome P450 isoenzyme CYP3A4, with less than 10% being excreted renally (Kantola, Kivisto & Neuvonen, 1998);
7. With a once a day dose regimen, plasma concentrations of total inhibitors over a dosing interval achieved a steady state between the second and third days of therapy and were about 1.5 times those following a single dose (Vree, Dammers, Ulc, Horkovics-Kovats, Ryska et al., 2003). When Lovastatin is given under fasting conditions, plasma concentrations of total inhibitors were on average about two thirds those found when

Lovastatin was administered immediately after a standard test meal (Hsu, Spinler & Johnson, 1995; (Merck & Co., Inc, 2007).

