APPENDIX 6: Drugs & Other Components That Interact With Lovastatin

AVOID WHILE TAKING LOVASTATIN

CYP3A4/5 – Inducers	
Carbamazepine (Tegretol)	Phenytoin (Dilantin)
Dexamethasone	Primidone (Mysoline)
Ethosuximide (Zarontin)	Progesterone (all progestins)
Glucocorticoids	Rifabutin
Griseofulvin	Rifampin
Nafcillin	Rofecoxib
Nelfinavir (Viracept)	St John’s wort
Nevirapine (Viramune)	Sulfadimidine
Oxcarbazepine (Trileptal)	Sulfipyrazone
Phenobarbital	Troglitazone
Phenylbutazone	Rifapentine
	Modafinil
CYP3A4/5 – Inhibitors	
Amiodarone	Metronidazole
Anastrozole	Mibefradil
Azithromycin (Zithromax)	Miconazole
Cannabinoids	Nefazodone
Cimetidine (Tagamet)	Norfloxacin
Clarithromycin	Norfluoxetine
Clotrimazole	Omeprazole (Prilosec)
Cyclosporine	Oxiconazole
Danazol	Paroxetine
Delavirdine (Rescriptor)	Propoxyphene
Diethylthiocarbamate	Roxithromycin
Diltiazem	Quinidine
Dirithromycin	Quinine
Disulfiram	Quinupristin and dalfopristin
Entacapone	Ranitidine
Erythromycin	Ritonavir (Norvir)
Ethinyl estradiol	Saquinavir (Invirase)
Fluconazole (Diflucan)	Sertindole
Fluoxetine	Sertraline
Fluvoxamine	Troleandomycin
Gestodene	Valproic acid (Depakote)
Grapefruit juice	Verapamil
Indinavir (Crixivan)	Voriconazole
Isoniazid	Zafirlukast (Accolate)
Itraconazole	Zileuton
Ketoconazole	

ADAPTED from Cytochrome P-450 Enzymes and Drug Metabolism: Lacy CF, Armstrong LL, Goldman MP, eds. Drug Information Handbook 8th ed. Hudson, OH; LexiComp Inc. 2000: 1364-1371.

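### The birth control entry condition in Section 4.2 is not reconciled with the avoid list in Appendix 6, which bars hormones used in contraceptives without exempting that use

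*Protocol*

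**What the plan says.** Section 4.2 of the protocol sets three conditions for female participants of childbearing age: not pregnant, a negative test before treatment starts, "and take appropriate birth control precautions to participate in this study". Nothing in the section says which precautions count as appropriate.

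Section 5.2.1 says every participant receives a full list of interacting medications and products "that must be completely avoided while being treated with Lovastatin", and points to Appendix 6. Appendix 6 is headed "AVOID WHILE TAKING LOVASTATIN". Among the CYP3A4/5 inducers it lists "Progesterone (all progestins"). Among the inhibitors it lists "Ethinyl estradiol" and gestodene. No entry carries a note on contraceptive use.

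A list also appears at the pre-treatment history and examination in Section 5.1.2: "Patients will also be given a list of medications to avoid while on this study".

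Section 4.3 excludes pregnancy and breastfeeding but says nothing about hormonal products. Section 5.1.3 and Appendix 3 schedule pregnancy tests before treatment and at weeks 8 and 16. The only other pregnancy text, in Appendix 10 for UK sites, deals with follow-up once a pregnancy has occurred. The SAP does not touch the subject.

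**The concern.** Two operating rules meet in the same participant and neither refers to the other. One makes birth control a condition of taking part. The other tells her to avoid, without exception, hormones that contraceptives contain.

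Two things are at stake, one for each way of resolving the clash:

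- **If the list prevails**, a girl may stop the method on which she entered. Section 6.1 reports that "Animal studies demonstrated that Lovastatin crossed the blood brain and placental barriers", and the protocol treats pregnancy as an exclusion and tests for it repeatedly. A family hand-out that can be read as an instruction to stop contraception works against that protection.
- **If Section 4.2 prevails**, she stays on a product that the protocol classes as an inducer or inhibitor of CYP3A4/5. Section 6.1 names CYP3A4 as the enzyme that metabolises lovastatin. Her exposure to study drug may then differ from that of other participants, in a direction that depends on the product.

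Without a rule in the text, each site has to decide for itself, and sites may decide differently.

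**Working it through.** No alpha, power, rate or sample size enters this point and the plan gives no figure to reproduce. The check sets the passages side by side.

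1. **Entry rule (Section 4.2).** Birth control precautions are required. No method is named or ruled out, and Appendix 6 is not mentioned.
2. **Treatment rule (Section 5.2.1 with Appendix 6).** The complete-avoidance wording is in Section 5.2.1; the appendix itself says only to avoid. The listed hormones are all progestins, ethinyl estradiol and gestodene. I found no exemption in either place.
3. **Link between them.** That these substances are components of hormonal contraceptives is common knowledge and is not stated in the protocol. Because the entry covers all progestins, a hormonal method is likely to fall under the list.
4. **Bridging rule (Section 4.3).** There is none for hormones. By contrast, psychotropic drugs, several of which are on the Appendix 6 list (for example fluoxetine, sertraline and carbamazepine), are dealt with at eligibility: Section 4.3 excludes them or requires at least 30 days off, and Section 6.4 gives interaction with lovastatin metabolism as one reason. The protocol aligned eligibility with the list for that class and not for this one.

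Applying rules 1 and 2 to each case:

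| Participant of childbearing age | Section 4.2 | Section 5.2.1 / Appendix 6 |
|---|---|---|
| Hormonal method, continued | met | breached |
| Hormonal method stopped, nothing in its place | not met | met |
| Hormonal method stopped, unlisted precaution used | met | met |
| Non-hormonal precaution throughout (or abstinence, if it counts as appropriate) | met | met |

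The first two rows are the conflict. The last two show its limit.

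**Timing.** Section 5.1.2 gives a list before treatment, as part of screening, and Section 5.1.5 randomises only after a successful screening period. The clash can therefore surface before randomisation, but the protocol gives no instruction for settling it at that point.

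**Number affected.** Planned enrolment is 142, aged 8 to under 16. The documents give no split by sex, no proportion of childbearing age and no rate of hormonal use, so no count can be derived.

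**The case against.** The strongest reply is that the two rules do not contradict each other. Section 4.2 neither requires nor mentions a hormonal method, and the word appropriate can be read together with the avoid list. Any unlisted precaution meets both. This stands against a stronger reading that a reader might infer, namely that a girl on hormonal contraception cannot comply at all. She can, by using another precaution. The reply does not dispose of the point, because the protocol never says that this is what she must do. As written, she enters validly on a method that the treatment rule then bars.

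Other replies carry some weight:

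- A list is handed over at pre-treatment, so it would be wrong to infer that girls first learn of it after randomisation.
- Withdrawal under Section 5.2.3 is not automatic. It refers to serious violation or non-compliance, as judged by the investigator or research team.
- The placental finding comes from animal studies, and the scheduled pregnancy tests are a real safeguard. They detect a pregnancy; they do not prevent one.
- Most Appendix 6 products have no matching exclusion and are handled by the list alone. What distinguishes the hormones is that another section makes birth control a condition of entry.
- Consent pages are not in the public text, and Appendix 4 is left for site-specific forms. Contraceptive advice may be given there. It would not reconcile the protocol's own sections.

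**Conclusion.** The point holds in limited form. For a girl whose birth control is hormonal, Section 4.2 and Section 5.2.1 with Appendix 6 give instructions that clash unless she moves to an unlisted precaution, and the protocol does not tell her or the site to do so. Girls using non-hormonal precautions are unaffected.

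The size is unknown. In this age range it may be small, possibly nil. A reader might be tempted to count all girls past menarche as affected. The documents do not support that, because only users of a listed hormone face the conflict.

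The conclusion rests on the protocol's wording plus one outside premise, that the listed hormones are used in contraceptives. It does not threaten the primary analysis. It is a safety and consistency matter, worth correcting because the text is easily mended and the participants are children.

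**What to change.** The sponsor should reconcile Sections 4.2, 4.3 and 5.2.1 and Appendix 6 so that the birth control condition and the avoid list agree and each refers to the other. The same reconciled wording should go onto the list given to families under Sections 5.1.2 and 5.2.1, and site consent forms should be checked against it. Which contraceptive or interaction rule stands is for the sponsor to decide; none is proposed here.

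The cost is a sentence or two in the eligibility sections, a note in Appendix 6 and an edit to the hand-out. Depending on the sponsor's choice, a few girls may be affected in eligibility or in method. Nothing in the sample size or the analysis needs to change.

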4.3 Exclusion Criteria

- Full-scale IQ less than 70. In cases where there is a statistically significant difference between performance IQ and verbal IQ (.05 level), patients will be excluded if both quotients fall below 70;
- Individuals that are not cognitively impaired on at least one of the primary objective outcome measures;
- Individuals with insufficient English to complete the assessments;
- Participants taking psychotropic medication other than methylphenidate and/or dextroamphetamines (see Section 4.2). Appendix 2 contains a list of common psychotropic medications. These patients are eligible if, as clinically indicated, they cease medication for at least 30 days prior to screening and remain off these medications for the duration of the study;
- Participants with intracranial pathology such as epilepsy, diagnosed head injury, hydrocephalus or progressive intracranial tumors (children with asymptomatic or static lesions will be eligible);
- Participants who are pregnant or breastfeeding;
- Participants who have received any investigational drug (other than sirolimus) within 30 days of screening;
- Participants who have recently taken sirolimus. These participants will be eligible after a washout period of at least three months;
- Participants who have recently taken Lovastatin. These participants will be eligible after a washout period of at least three months;
- Participants with significant hepatic, renal or hematologic function as previously defined;
- Participants with a history of neuromuscular disease, excluding hypotonias thought to be associated with NF1;
- Participants with a clinically significant unrelated illness, which in the judgment of the principal or associate investigator, would compromise the participant's ability to tolerate the medication or potentially interfere with the participant's ability to participate in the required testing;
- Low cholesterol (lower limit of a total cholesterol of 90mg/dl).

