6.3 Procedures/Recommendations for Drug Supply and Distribution

Lovastatin and its matching placebo will be obtained and distributed to participating sites by a subcontractor to the Operations Center. A 20mg tablet of Lovastatin or an identical tablet (placebo) will be provided for each participant. Medications, including the placebo, will be provided to the participants free of charge. Participants will be instructed to return all unused medications as well as empty bottles at each clinic visit. All unused medicine will be disposed of properly at each individual site.

Lovastatin is administered orally. The bioavailability of the tablet increases under the influence of a meal. Based on these findings, it is advised to take the tablets immediately after a meal. One dose per day after dinner time will be instructed to parents, since evening doses are more effective than the same dose given in the morning (Merck & Co., Inc, 2007). Lovastatin is a substrate for cytochrome P450 isoform 3A4 (CYP3A4). Grapefruit juice contains one or more components that inhibit CYP3A4 and can increase the dose concentration. Participants will be instructed to avoid the consumption of grapefruit juice during the treatment. A complete list of drug interactions/contraindications will be described to parents and participants.

Compliance will be monitored by recording the number of pills dispensed to families from the pharmacy and then comparing that to the number of pills that are returned at each monthly visit. Participants will be asked to return all unused pills at each visit. A pill diary will also be maintained by each participant and reviewed at each follow-up visit to ensure compliance with the medication.

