6.11 Risks and Protection from Risks

Individual risks in this study are associated with the use of Lovastatin, laboratory tests (blood drawn) and with neuropsychological testing.

Lovastatin has been shown to be safe and effective in a pediatric population for treatment of familial HeFH. The FDA has approved Lovastatin (40mg/day) for treatment of HeFH in children and it is believed to be safe to extend to other potential uses. The most frequent side effects of Lovastatin are muscular pains, weakness and tenderness, and gastrointestinal conditions such as

abdominal pain, flatulence, diarrhea and constipation, and are reversible once the medication has been discontinued. Participants will be provided with a list of drug and food items that they should avoid while on study medication. All participants will be monitored for adverse events as described in Section 6.7. Participants who experience adverse events related to the study medication will have study medication withheld and/or modified as outlined in Section 6.6. Additionally, there will be regular monitoring and clinical evaluation.

In the 24 patients that were evaluated for the Phase 1 Lovastatin study, few patients' total cholesterol dropped below 100, and in all cases, the HDL:LDL ratio was within normal limits. In all cases total cholesterol returned to baseline after the treatment. From a clinical perspective, decreased LDL is one of the desirable outcomes of using Lovastatin. There is no evidence of increase risk or harmful consequences for a temporal decrease of LDL levels. Since this is a 16 week study (plus follow-up), transient decrease in lipid profile levels will not change the risk for this patient population.

Since the long-term effects of lowering lipid levels in the children on Lovastatin are unknown at this time, having normal range cholesterol (cholesterol \geq 90 mg/dL) is a criteria for enrollment. In addition, a lipid profile is checked at baseline and at weeks 4, 8, 12, 16 and 24. If levels drop below 80 mg/dL, the site should notify the protocol team for guidance. If other lipid profile levels drop below normal values, the site should also notify the protocol team for guidance.

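### Appendix 6, the avoid list that Section 5.2.1 calls complete, omits gemfibrozil, and no rule bars taking gemfibrozil or a second statin during treatment

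*Protocol*

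**What the plan says.** Four places in the protocol promise families a list of products to avoid.

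- Section 5.1.2, at the screening history: "Patients will also be given a list of medications to avoid while on this study".
- Section 5.2.1, at dispensing: "All participants will be provided with a complete list of medications and products that have detrimental interactions with Lovastatin". It says these must be avoided altogether during treatment and refers to Appendix 6.
- Section 6.3: "A complete list of drug interactions/contraindications will be described to parents and participants".
- Section 6.11: "Participants will be provided with a list of drug and food items that they should avoid while on study medication".

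One lovastatin interaction list is supplied. It is Appendix 6, headed "AVOID WHILE TAKING LOVASTATIN" and divided into CYP3A4/5 inducers and CYP3A4/5 inhibitors. Appendix 2 lists psychotropic drugs only.

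On eligibility, the only lipid-lowering drug that Section 4.3 names is lovastatin itself: "Participants who have recently taken Lovastatin. These participants will be eligible after a washout period of at least three months". The same section has a 30-day rule for investigational drugs, rules on psychotropics and sirolimus, a cholesterol floor of 90 mg/dl, and an item left to discretion: "Participants with a clinically significant unrelated illness, which in the judgment of the principal or associate investigator" would compromise tolerance of the drug or participation in testing.

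Section 1.7 puts lovastatin myopathy or marked CPK elevation below 1 in 500 among people treated for hypercholesterolemia and cites two papers. In Section 10.0 the title of one attributes rhabdomyolysis with kidney failure to lovastatin combined with gemfibrozil. The title of the other links the same pair to myopathy and rhabdomyolysis. Gemfibrozil appears nowhere else in the documents.

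**The concern.** A list that the protocol calls complete will be used as complete. A family or a site pharmacist who checks gemfibrozil against Appendix 6 will not find it and may reasonably conclude that it is allowed. The protocol's own references point the other way, since both papers behind its myopathy figure concern this combination. The plan is therefore inconsistent with itself on a muscle-safety question, in children who will take 40 mg/day for 14 weeks.

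The stake is safety in the rare child who takes gemfibrozil on entry or is prescribed it during treatment. The primary and secondary efficacy comparisons are not at issue.

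**Working it through.** The plan gives no figure on this point to reproduce. The check compares the texts, with one count and one timing.

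**1. Contents of Appendix 6.** The inducer block has 11 full rows of two plus one single entry: 11 × 2 + 1 = 23. The inhibitor block has 25 full rows of two plus one single entry: 25 × 2 + 1 = 51. The total is 23 + 51 = 74. A search of the entries for statin, fibrate, niacin and nicotinic acid names finds 0. The appendix says it was adapted from a general table of cytochrome P-450 enzymes and drug metabolism. Such a table can be full for that mechanism and still fall short of what 5.2.1 promises, which is every product with a harmful interaction.

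**2. Rules that might bar the combination anyway.**

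| Rule | Does it reach concurrent gemfibrozil or a second statin? |
|---|---|
| 4.3, lovastatin washout | No. It covers past use of lovastatin only. |
| 4.3, investigational drugs within 30 days | Not if the drug is an ordinary prescription. |
| 4.3 and 6.4, psychotropics and anticonvulsants | No. |
| 4.3, unrelated illness | Only by judgment, and it turns on an illness rather than a drug. |
| 4.2, medically stable | Only by judgment. |
| 4.3 and 6.11, cholesterol | No. 6.11 speaks of "having normal range cholesterol", but the criterion is a floor of 90 mg/dL with no upper limit. |
| 5.2.3, off-study criteria | No lipid-drug item. Changes of stimulant are named; otherwise the team may act in the child's best interest. |
| SAP | No rule on concomitant drugs. |

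**3. Protections around the first dose.** Before dosing there are a medical history and examination (5.1.2); a fasting lipid profile, CPK and liver tests (5.1.3); and a liver-function criterion (4.2). These give a physician the chance to notice, but none is a rule on the drug.

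After dosing there are a week 2 phone check (Appendix 3), prompt reporting of muscle symptoms with stopping if myopathy is suspected (6.5.2), dose holds (6.6) and CPK every four weeks ± 4 days (5.2.2).

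The first on-treatment CPK is due on day 28 ± 4, that is day 24 to day 32. The first 14 days are at 20 mg, so it comes after 24 − 14 = 10 to 32 − 14 = 18 days at 40 mg.

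**4. Size.** The documents do not say how many candidates take gemfibrozil or another statin, and they do not give the added muscle risk of either combination. The figure of less than 1 in 500 describes lovastatin therapy in hypercholesterolemia and cannot stand in for that added risk. One could assume a number of exposed children and compute the chance that one is assigned lovastatin. That would restate the allocation ratio and say nothing about harm, so no probability is offered.

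**The case against.** The best reply is that the case hardly arises. Nothing in the documents suggests that any candidate aged 8 to 15 takes gemfibrozil. The evidence is two reference titles, not the papers. A physician takes a full history before dosing. The lists promised in 5.1.2, 6.3 and 6.11 are not tied to Appendix 6, and the one in 6.3 is to cover contraindications as well as interactions, so what families receive may be broader than the appendix. All of this stands, and it keeps the point minor. It does not remove the mismatch in 5.2.1, which ties its complete list to Appendix 6. Discretion and unseen hand-outs are also not a written bar.

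Three stronger readings are tempting, and the documents do not support them.

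- A reader might infer that the three-month washout should extend to every statin. A washout addresses past use, whereas the harm at issue comes from taking the drugs together. The documents give no basis for that interval for other statins. The nearest figure, in Section 5.4, is cholesterol returning to normal about 30 days after high-dose lovastatin.
- A reader might infer that a second statin is as well documented a hazard as gemfibrozil. No reference title says so. The 40 mg/day maximum in 6.4 is for lovastatin, not for the class. Section 1.7 mentions adult doses up to 80 mg/day, and much higher short-course doses in adults with cancer, where myopathy was dose-limiting.
- A reader might infer that investigator judgment alone stands before the first dose. The pre-dose history, laboratory tests and promised lists show otherwise.

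**Conclusion.** The point holds as a minor safety correction. Appendix 6 is not the complete list that Section 5.2.1 says it is, and the omission that the documents themselves expose is gemfibrozil. No eligibility or on-treatment rule bars concurrent gemfibrozil or a second HMG-CoA reductase inhibitor. The gemfibrozil part rests on the protocol's own reference titles. The second-statin part is a precaution only.

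The conclusion assumes that the supplied text contains every rule on concomitant drugs and that Appendix 6 is the list meant in 5.2.1. Frequency of exposure and added risk are both unknown, and exposure is probably very rare.

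**What to change.** 1. Add gemfibrozil to Appendix 6 and to the hand-out for families, under a heading separate from the two CYP3A4/5 blocks.
2. State in Sections 4.3 and 5.2.1 that gemfibrozil may not be taken during treatment. In the same sentence, as a precaution, bar any HMG-CoA reductase inhibitor other than study drug. For example: *Gemfibrozil, and any HMG-CoA reductase inhibitor other than study medication, are not permitted during the treatment period.*
3. Leave the lovastatin washout in 4.3 as it is.

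The cost is one sentence in two sections, an added entry in the appendix and an updated hand-out. No visit or test is added, because the medical history and the avoid list are already part of screening. The downside is that a rare child who needs such a drug is excluded.
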